# Amendment 3 (Version 4)

Section of the SAP	Summary of Change	Rationale
3.3. Other Endpoints	Updated to reflect the addition of NT-proBNP and Troponin I	Updated to be consistent with protocol amendment 4
3.4. Baseline Variables	Updated to specify the definition of baseline for NT-proBNP and Troponin I	Updated to specify the definition of baseline for NT-proBNP and Troponin I
5.3. Methods to Manage Missing Data	Clarify that missing data from Cohort A subjects who ended participation in the study and returned subsequently will not be imputed	Updated to reflect the protocol administrative letter (PACL) issued on November 26, 2019 allowing Cohort A subjects who ended participation to return to the study
6.2.3. Kansas City Cardiomyopathy Questionnaire	Clarified the treatment groups to be used in the analysis of KCCQ related endpoints	Updated to clarify the treatment groups to be analyzed
6.2.6. NT-proBNP and Troponin I	Specific analyses for the 2 endpoints (NT-proBNP and Troponin -I) added in protocol amendment 4	Updated to be consistent with protocol amendment 4
6.5.1. Adverse Events	Clarify how adverse events from Cohort A subjects who ended participation in the study and returned subsequently will be handled	Updated to reflect the protocol administrative letter (PACL) issued on November 26, 2019 allowing Cohort A subjects who ended participation to return to the study.
Section 9. APPENDICES	Summary of analyses table in Appendix 1 and definition and use of visit windows in reporting in Appendix 1.1. updated to reflect the addition of NT-proBNP and Troponin I	Updated to be consistent with protocol amendment 4

#### Amendment 4 (Version 5)

Section of the SAP	Summary of Change	Rationale
Various Sections listed below.	Removed extra spaces and/or updated text to correct typos	Removed extra spaces and/or updated text to correct typos
2.1. Study Objectives		
3.3. Other Endpoints		
3.4. Baseline Variables		
4.4. Other Analysis Sets		
6.2.1. Cardiovascular-related mortality		

#### DMB02-GSOP-RF02 3.0 STATISTICAL ANALYSIS PLAN TEMPLATE 30-Jun-2015 PFIZER CONFIDENTIAL Page 8 TMF Doc ID: 98.03

Section of the SAP	Summary of Change	Rationale
6.3. Subset Analyses		
6.4. Baseline and Other Summaries and Analyses		
6.5.1. Adverse Events		
Appendix 1.1. Definition and Use of Visit Windows in Reporting		
6.5.2. Laboratory Data	Added analyses of laboratory data excluding site 1121	Updated to address a potential quality issue at site 1121
6.5.4. Physical Examinations and Vital Signs	Added analyses of vital signs data excluding site 1121	Updated to address a potential quality issue at site 1121
Appendix 1.1. Definition and Use of Visit Windows in Reporting	Added a paragraph describing calculation of visit windows for KCCQ, NT-proBNP, Troponin I endpoints	KCCQ, NT-proBNP, Troponin I analyses will combine data from B3461028. Clarification was provided on how visit windows will be re-calculated for all study visits from B3461045

#### **2. INTRODUCTION**

This SAP provides the detailed methodology for summary and statistical analyses of the data collected in Study B3461045. This document may modify the plans outlined in the protocol; however, any major modifications of the primary endpoint definition or its analysis will also be reflected in a protocol amendment.

# 2.1. Study Objectives

# Primary Objectives:

- To obtain additional, long-term, safety data for tafamidis in subjects with transthyretin amyloid cardiomyopathy (ATTR-CM).
- To provide investigational product, tafamidis, to enrolled subjects until local availability by prescription for the ATTR-CM indication.

# 2.2. Study Design

This is a Phase 3, open-label long-term extension safety study designed to obtain additional safety data for tafamidis meglumine 20 mg and 80 mg (or tafamidis 61 mg where available), and to continue to provide enrolled subjects with tafamidis for up to 60 months, or until subject has access to tafamidis for ATTR-CM via prescription, whichever occurs first. The study will also end before 60 months if the sponsor discontinues the study. Subjects withdrawn from the study due to commercial access to prescription tafamidis in their

DMB02-GSOP-RF02 3.0 STATISTICAL ANALYSIS PLAN TEMPLATE 30-Jun-2015 PFIZER CONFIDENTIAL Page 9 TMF Doc ID: 98.03 respective countries will be considered study completers. The decision to withdraw subjects for transition to commercial tafamidis will be made by the sponsor.

Eligible study participants will be enrolled in 2 Cohorts:

- Cohort A Subjects diagnosed with ATTR-CM who completed 30 months of participation in Study B3461028.
- Cohort B Subjects diagnosed with ATTR-CM who have not previously participated in Study B3461028.

Cohort A subjects receiving tafamidis meglumine 20 mg or 80 mg will be assigned to tafamidis 61 mg, once daily, in addition to standard of care (eg, diuretics), for up to 60 months. Subjects will be assigned to tafamidis meglumine 80 mg in regions where 61 mg tafamidis is unavailable.

At enrollment, subjects in Cohort B will be assigned to open label 61 mg tafamidis once daily, in addition to standard of care (eg, diuretics), for up to 60 months. One dose reduction to 20 mg tafamidis meglumine will be permitted for adverse events related to tolerability. Subjects will be assigned to 80 mg tafamidis meglumine in regions where 61 mg tafamidis is unavailable.

# **3. ENDPOINTS AND BASELINE VARIABLES: DEFINITIONS AND CONVENTIONS**

# 3.1. Primary Endpoint(s)

Safety as measured by:

- All-cause mortality.
- Incidence of treatment-emergent adverse events.

# 3.2. Secondary Endpoint(s)

Not Applicable.

#### 3.3. Other Endpoints

- *Cardiovascular-related mortality.*
- Frequency of all-cause hospitalization.
- Frequency of cardiovascular-related hospitalization (including heart failure, arrhythmia, myocardial infarction, stroke and other cardiovascular-related events).
- Change from baseline at each visit in Kansas City Cardiomyopathy Questionnaire Overall Score and domain scores (Physical limitation, Symptom stability, Symptom frequency, Symptom burden, Total symptom, Self-efficacy, Social limitation, and Quality of life) and Clinical summary score.
- New York Heart Association classification at each visit.
- Change from baseline in Body Mass Index/modified Body Mass Index at each visit.
- Change from baseline in N-terminal pro-hormone brain natriuretic peptide (NT-proBNP) concentration at each visit.
- Change from baseline in Troponin I concentration at each visit.
- Assessment of physical examinations, use of concomitant medications, electrocardiograms (ECGs), clinical laboratory testing, vital signs at each visit.

# 3.4. Baseline Variables

Cohort A Subjects: In the analyses of Cohort A subjects, for all endpoints except for all-cause and cardiovascular-related mortality, KCCQ, NT-proBNP, and Troponin I, Day 0 of the subjects participation in Study B3461045 will be used as baseline.

For time to event endpoints, ie, all-cause mortality and cardiovascular related mortality, the data from Study B3461028 will be included in the time to event analysis. Therefore, the baseline for Study B3461028 will be used as the start time in the time to event analyses.

 Table 2.
 Summary of Definition for Baseline Values

Endpoints	Baseline Definition
All endpoints except for mortality, KCCQ, NT-proBNP, Troponin I	Last observation prior to the subject receiving B3461045 study treatment.
All-cause and cardiovascular-related mortality,KCCQ (overall and domain scores), NT-proBNP, Troponin I	Study day corresponding to baseline measurement in the preceding double-blind study B3461028 will be used as the start time in all the mortality based analysis and as baseline for the KCCQ based endpoints (overall, domain, and clinical summary scores), NT-proBNP, Troponin I

Cohort B Subjects: In all the analyses of Cohort B subjects, Day 0 of the subjects participation in Study B3461045 will be used as baseline.

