6.1. Screening Visit

6.1.1. Screening Visit Cohort A (Day 0)

Screening Visit (Day 0) is the Month 30 End of Study visit and last day of treatment for Study B3461028. Study procedures and assessments will be performed once per subject and the protocol-specified data will be reported separately for each study. Subjects providing consent and fulfilling the inclusion/exclusion criteria will be enrolled, randomized, and dispensed study medication for Study B3461045 at the same visit. Subjects will be instructed to start self-administration of tafamidis the following day (Day 1).

If more than 30 days have elapsed from the B3461028 End of Study visit, then vital signs, a brief physical examination, clinical laboratory tests, contraception check, concomitant medications, adverse event reporting must be performed on Day 0 prior to enrollment.

Written subject informed consent will be obtained prior to any study-related procedures.

The following procedures will be conducted during the Screening/Day 0 visit:

- All inclusion and exclusion criteria will be reviewed to ensure eligibility for participation in this study [Study B3461045 only].
- Demography (date of birth, age, gender and race) [Study B3461045 only].
- Complete medical history (including history of heart failure) [Study B3461045 only].
- Full physical examination including weight and height measurements will be performed. If more than 30 days have elapsed from the B3461028 Month 30 End of Study visit, then a brief physical examination must be performed on Day 0.
- Measure vital signs (systolic and diastolic blood pressure supine and standing, pulse rate supine and standing, respiration rate, and body temperature).

- Single 12-lead ECG perform ECG prior to any blood collection or blood pressure measurements.
- Collect blood, and urine samples for the following clinical laboratories. If more than 30 days have elapsed from the B3461028 Month 30 End of Study visit, then a new set of clinical laboratory tests must be performed prior to enrollment and randomization.
 - Hematology;
 - Serum Chemistry;
 - Coagulation (International normalized ratio [INR], Prothrombin time [PT]);
 - Urinalysis;
 - Urine pregnancy test for women of childbearing potential;
 - Follicle-stimulating hormone (FSH) test for female subjects of non-childbearing
 potential who have not had a hysterectomy, bilateral oophorectomy, or medically
 confirmed ovarian failure. Subjects who already confirmed menopause with an

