9.2.6. Cardiac Biomarkers NT-proBNP and Troponin I

For Cohorts A and B, descriptive statistics for change from baseline (initiation of tafamidis) in NT-proBNP and Troponin I concentration will be summarized.

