# 6.2.6. NT-proBNP and Troponin I

For Cohort A, as defined in Section 3.4, the baseline for Study B3461028 will be used as the baseline for all NT-proBNP and Troponin I based analyses. Change from baseline for all visits, including the visits from Study B3461028 will be summarized descriptively for NT-proBNP and Troponin I by treatment group (tafamidis/tafamidis and placebo/tafamidis).

For Cohort B, descriptive statistics for change from baseline at each post-baseline visit will be provided for NT-proBNP and Troponin I.

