#### Appendix 1.1. Definition and Use of Visit Windows in Reporting

For the purpose of this study, Day 1 is defined as the first dose day under this protocol (except for mortality-based endpoints, KCCQ, NT-proBNP, and Troponin I).

The following describes the clinical visit windows allowed within the protocol:

Clinic Visits (Months 6, 12, 18, 24, 30, 36, 42, 48, 54) ±2 weeks

End of Study Visit (Month 60) ±2 weeks or Early Study Discontinuation

However, in order to maximize the use of all available data, the visit windows for each visit are expanded as follows:

Clinic Visits (Months 6, 12, 18, 24, 30, 36, 42, 48, 54) ±3 months

All nominal visits (months 6, 12, 18, 24, 30, 36, 42, 48, 54) will use the data as collected from that visit. Early termination visits will never replace an existing visit. If the visit covered by the windowing rules above is already populated with an existing nominal visit, then the early termination visit should be mapped forward to the next 6 month visit.

Data from endpoints that are collected at "Month 3" either in France or Germany as part of the country-specific protocol amendment will be summarized descriptively as 'Month 3- Unscheduled' and will not be subject to the windowing rules described above.

Analyses of KCCQ, NT-proBNP, Troponin I will combine data from B3461028 study. For these endpoints, visits for B3461045 will be evaluated as "30 Months" plus the visit window calculated using the B3461045 windowing rules specified above.

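### For placebo/tafamidis subjects, the SAP takes NT-proBNP and troponin I change from the parent-study baseline, while protocol 9.2.6 takes it from the start of tafamidis

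*SAP*

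**What the plan says.** Protocol 9.2.6 covers both cohorts: "descriptive statistics for change from baseline (initiation of tafamidis) in NT-proBNP and Troponin I concentration will be summarized".

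SAP 3.4 sets the Cohort A baseline "for all endpoints except for all-cause and cardiovascular-related mortality, KCCQ, NT-proBNP, and Troponin I, Day 0 of the subjects participation in Study B3461045", so mortality, KCCQ and the two biomarkers are excepted from the Day 0 rule. For these, Table 2 uses the parent-study baseline measurement, which serves "as baseline for the KCCQ based endpoints (overall, domain, and clinical summary scores), NT-proBNP, Troponin I". SAP 6.2.6 repeats this for Cohort A: "the baseline for Study B3461028 will be used as the baseline for all NT-proBNP and Troponin I based analyses". It then describes the display: "Change from baseline for all visits, including the visits from Study B3461028 will be summarized descriptively for NT-proBNP and Troponin I by treatment group".

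SAP Appendix 1.1 dates extension visits for these endpoints as 30 months "plus the visit window calculated using the B3461045 windowing rules specified above".

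In the SAP change log for Amendment 3 (Version 4), the row for section 3.4 says that the biomarker baseline was specified. The row for 6.2.6 gives as its reason "Updated to be consistent with protocol amendment 4". Neither row mentions a difference from protocol 9.2.6.

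**The concern.** Placebo/tafamidis subjects start tafamidis only on entering B3461045 (protocol 5.1.1), after a 30-month placebo-controlled parent study (protocol 1.2). For them the parent baseline is the start of placebo, so the two documents name different quantities under the same label.

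A reader who takes the protocol's definition to the SAP's table would read an extension value in this group as the change since starting tafamidis. It is in fact the change since starting placebo. The quantity that 9.2.6 names would appear nowhere in the report for this group.

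**Working it through.** **Side by side, by group**

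| Group | Protocol 9.2.6 baseline | SAP 3.4 / 6.2.6 baseline | Same? |
|---|---|---|---|
| Cohort A, tafamidis/tafamidis | Start of tafamidis, in B3461028 | B3461028 baseline | Yes |
| Cohort A, placebo/tafamidis | Start of tafamidis, on entry to B3461045 | B3461028 baseline, the start of placebo | No, about 30 months apart |
| Cohort B | Start of tafamidis | Day 0 of B3461045 | Yes |

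**Length of the interval for placebo/tafamidis**

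Inputs: the parent study lasted 30 months (protocol 1.2), and extension Month m is dated 30 + m (SAP Appendix 1.1).

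Nominal share of the interval spent on placebo = 30 / (30 + m).

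- Month 42: 30/72 = 41.7%.
- Month 60: 30/90 = 33.3%.

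Under protocol 9.2.6 the interval would be m months and the share 0%.

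**Which visits can hold data**

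Extension sampling of the biomarkers began only after Amendment 4 (protocol 7.6; Schedule of Activities, note x). The original protocol is dated 29 January 2016 and Amendment 4 is dated 09 August 2019 (SAP section 1). The gap is 1288 days, and 1288/30.4375 = 42.3 months. A subject enrolled on the first conceivable day would therefore contribute extension values only from about Month 42. Later enrollees would contribute from earlier visits, where the share is larger. Enrolment dates are not given, so the documents do not show how many values exist at any earlier visit.

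**Can the planned display supply the missing quantity?**

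SAP 6.2.6 shows parent and extension visits, each as change from the parent baseline. Subtracting the group mean at a late parent visit from the mean at an extension visit is not a within-subject change unless the same subjects contribute to both. Medians cannot be subtracted in this way at all. So the planned output does not give it.

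**Is a value before the first tafamidis dose available?**

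Protocol 6.1.1 states: "Screening Visit (Day 0) is the Month 30 End of Study visit and last day of treatment for Study B3461028". A Month 30 parent sample, if one was taken, would therefore usually fall just before the first tafamidis dose. There are two limits.

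- The same section allows for more than 30 days between the parent End of Study visit and Day 0, so the two dates need not coincide.
- The documents do not say at which parent visits the biomarkers were sampled.

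A separate extension draw on Day 0 is not expected for Cohort A. Its Day 0 list in 6.1.1 omits the biomarkers, while the Cohort B lists in 6.1.2 and 6.1.4 include them. Cohort A was also enrolled under blinded assignment, which gave way to open label after Amendment 3, before biomarker sampling began. This is an inference, because the Schedule of Activities marks a Day 0 draw in the column that Cohort A shares with part of Cohort B.

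**The case against.** The strongest reply is that the SAP's choice is permitted, deliberate and clear. Protocol section 9 and SAP section 2 both let the SAP change the protocol's plan, and only major changes to the primary endpoint or its analysis must also go into a protocol amendment. These biomarkers are descriptive other endpoints without a hypothesis test (SAP 5.1). SAP 3.4, 6.2.6 and Appendix 1.1 agree with each other, so a programmer would not be misled. All of this stands. A reader might infer a breach of the amendment rule, and the documents do not support that.

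A reader might also infer that the baseline was changed silently. That goes too far. The change log has its own row saying that the biomarker baseline was specified. What it lacks is a statement that this differs from 9.2.6.

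A third temptation is to quote early visits, such as extension Month 6, where 30/36 = 83% of the interval is on placebo. Because sampling began after Amendment 4, such visits may hold few or no placebo/tafamidis values.

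Finally, the SAP rests on Amendment 4, while the protocol supplied contains text introduced with Amendment 5 (Schedule of Activities, note y). The Amendment 4 wording of 9.2.6 cannot be checked, so the two may have matched when the SAP was written. The mismatch between the documents as supplied remains.

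**Conclusion.** The point holds as a discrepancy to reconcile, confined to placebo/tafamidis in Cohort A and to two descriptive endpoints. Extension changes in that group include about 30 months on placebo, nominally 42% of the interval at Month 42 and 33% at Month 60. These figures assume the nominal 30-month parent period and the SAP's visit dating. They say nothing about the size or direction of any biomarker difference. No p-value and no mortality analysis is affected.

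Two wider readings are not supported.

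- A reader might think Day 0 is the wrong baseline for laboratory, ECG, NYHA and BMI summaries in subjects already on tafamidis. The SAP applies it consistently, and a pre-drug baseline there would be a preference, not a correction.
- A reader might think SAP 3.5.1 removes recurrent events from the primary incidence of treatment-emergent adverse events. That depends on whether an event there means an episode or a coded term. If it means an episode, a new onset after resolution is a new event and nothing is lost. The text does not settle this, and the documents give no way to size it, so it is only a minor clarification.

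**What to change.** 1. Keep the by-visit display from the parent baseline in SAP 6.2.6. For placebo/tafamidis, add a descriptive within-subject change in NT-proBNP and troponin I from the last available value before the first tafamidis dose (a late parent visit, or Day 0 if sampled). State the gap from that value to the first dose and the number of subjects who have one.
2. Say in SAP 3.4 and 6.2.6 how the two baselines relate to protocol 9.2.6.
3. If no value before the first tafamidis dose exists, amend protocol 9.2.6 to match the SAP.
4. As a separate minor clarification, state in SAP 3.5.1 whether events are matched by episode or by coded term, and how a resolved event that recurs is counted.

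Cost: one extra descriptive table, possibly with incomplete values before tafamidis, or one protocol wording change. The clarification to 3.5.1 is a sentence or two. SAP 6.2.6 already brings the parent-study visits into this analysis, so the table needs no new data collection.

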#### 3.5. Safety Endpoints

#### 3.5.1. Adverse Events

An adverse event is considered treatment emergent in study B3461045 if:

- The event occurs during the "effective duration of treatment" (defined in Section 6.5.1) in Study B3461045 and was not seen prior to the start of treatment in the study B3461045, or
- The event was observed prior to the start of study B3461045 but increased in severity during treatment in Study B3461045.

#### 4. ANALYSIS SETS

#### 4.1. Full Analysis Set

Not Applicable.

# 4.2. Per Protocol Analysis Set

Not Applicable.

# 4.3. Safety Analysis Set

The safety analysis population consists of all subjects (Cohorts A and B) who are enrolled in this study and who have taken at least one dose of study treatment.

# 4.4. Other Analysis Sets

The "Combined Mortality Analysis Set" will include all subjects in the ITT-Analysis Set from B3461028. Mortality analyses in study B3461045 for Cohort A subjects will combine data from subjects in study B3461028, including subjects who died, discontinued in B3461028, or didn't enroll into B3461045 (ie, ITT Analysis Set from B3461028) with mortality data through participation in the B3461045 study. This analysis set will be referred to as "Combined Mortality Analysis Set".

